- 8.7. For patients that PANO is discontinued due to GVHD they are allowed to continue to be ON study. All assessment, procedures, CRF forms, correlative studies (appendix F) will be performed identically to patients that continue to take PANO and we will not deviate from what is stipulated in the protocol for patients that are receiving study drug on study.
- 8.8. Special considerations for toxicity observed up to day +7 post transplant: Due to unknown interactions between conditioning regimen and PANO, guidance is provided between PANO 1st dose to day +7 HCT as follows:
 - 8.8.1. PANO will be stopped for any non-hematological CTCAE (v4) grade 3 or higher toxicities unexpected for HCT (see table 8) seen between first dose of study drug and day +7 post-HCT. If there is complete reversal of toxicity, PANO can be resumed after 7 days and a minimum of one week off study drug and continued until completion of protocol-specified dosing schedule. In the absence of complete reversal of toxicity within 7 days, the study drug will be discontinued and the patient removed from the study. All such patients will remain evaluable for analysis and not replaced.

8.9. For gastrointestinal (GI) symptoms (diarrhea or nausea/vomiting) thought to be related to PANO from day -5/-6 to day +7 and/or after recovery from acute GI toxicity due to chemotherapy: The PANO dose may be modified according to the severity of the GI side effects as suggested and described in Table 6 and 7. Depending on the patients' clinical status, dose adjustments may be made within 1 week from when the lab work is completed. Patients who require PANO adjustment will have their dose HOLD for 3 doses and may resume 100% dosing thereafter at physician discretion. A trial of anti-emetics and anti-motility agents should be considered (institutional Clinical Practice Guidelines) before modifying the dose of PANO. In case patient regurgitate PANO pill will be allowed to re-dose after anti-emetics trial. PANO should continue for patients who develop GI symptoms related to infection.

Table 6. Management guidance for Diarrhea.

	Diarrhea Grade	PANO dose reduction
Mild	Grade 1: <4 stools/day over baseline	0%
Moderate	Grade 2: Increase 4-6 stools/day over baseline	0%
Severe	Grade 3: Increase >7 stools/day over baseline	No GI GVHD: hold only after failure of antimotility agents. Resume once the GI toxicity has resolved to grade 0-2 and continued until completion of protocol-specified dosing schedule If GI GVHD*

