9.1. AE definition: An adverse event (AE) is the appearance or worsening of any undesirable sign, symptom, or medical condition occurring after starting PANO that is unexpected with HCT. Table 8 describes criteria for “expected” toxicities for HCT/GVHD-related symptoms that are commonly observed in transplant patients. Certain Grade 4 toxicities under particular categories in the NCI CTCAE are common in the HCT transplant setting, and patients with Grade III or IV GVHD are likely to experience additional serious symptoms. These listed toxicities are likely related either to the HCT or preparatory and treatment regimens, however, the investigator must use best medical judgment in making an assessment as whether or not the study drug (PANO) may have had a contributory role.

Table 8. Expected Transplant/GVHD-Related Toxicities in HSC Transplant Patients.

Category	Symptoms/Event	Category	Symptom/Event
Dermatological	Pruritus Rash/dermatitis associated with high-dose chemotherapy or GVHD	Renal/Genitourinary	Bladder spasms/cystitis Creatinine elevation/renal failure Dysuria frequency-urgency Urinary retention
Constitutional	Fever, Rigors, Chills Headache Tremors Weight lost and gain Confusion due to medications Peripheral edema	Reproductive	Persistent amenorrhea
Gastrointestinal	Gastritis GERD Colitis Dehydration Diarrhea Nausea/vomiting Dysphagia Stomatitis/pharyngitis Hematocheza/melena Abdominal pain or cramping	Metabolic/Laboratory	Acidosis/alkalosis Amylase/lipase elevation Hypo-/Hyperglycemia Hypo-/Hyperkalemia Hypo-/hypercalcemia Hypo-/Hypermagnesium, Hypophosphatemia Hypo-/Hypernatremia Hypertriglyceridemia/Hyperlipidemia/hypercholesterolemia Hyperuricemia Increased LDH

Category	Symptoms/Event	Category	Symptom/Event
Hepatic	LFT elevation Bilirubin elevation Hypoalbuminemia Hepatomegaly	BMTComplex/ Multicomponent Events	GVHD* Stem-cell infusion complications Venoocclusive Disease/ascites
Cardio-vascular	Edema Hypertension/Hypotension Sinus tachycardia Arrhythmia (Atrial fibrillation/flutter; Sinus ventricular tachycardia and others) Vascular access complication- deep vein thrombosis requiring anticoagulation Thomboembolic event	Hematologic	Cytopenias Catheter associated venous thrombosis
Infections*	Bacterial, fungal and/or viral infections Sepsis/confusion		

*Infection and GVHD: These toxicities will not be considered AEs but data will be captured on eCRFs. Other toxicities will NOT be captured as expected HCT complications.

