 - 9.3.6.1. Routine treatment or monitoring of the studied indication, not associated with any deterioration in condition
 - 9.3.6.2. Elective or pre-planned treatment for a pre-existing condition that is unrelated to the indication under study and has not worsened since signing the informed consent
 - 9.3.6.3. Social reasons and respite care in the absence of any deterioration in the patient’s general condition
 - 9.3.6.4. Note that treatment on an emergency outpatient basis that does not result in hospital admission and involves an event not fulfilling any of the definitions of a SAE given above is not a serious adverse event
 - 9.3.7. Reporting: See section 11.7.

9.4. Special considerations for AE attribution:

- 9.4.1. Diarrhea:
 - 9.4.1.1. From PANO first dose to day +21 post-HCT attribution to study drug is difficult as majority of patients develop diarrhea as part of the conditioning regimen and/or rarely due to GVHD.
 - 9.4.1.2. After day + 22 post HCT, if a patient develops diarrhea grade 3 (increase more than 7 stools above baseline) or grade 4 (life threatening), excluding infection and/or GVHD, the AE is considered “probable” or “definitive” related to PANO. Protocol specific stopping rules have been formulated for excess GI toxicity (section 12.2).
- 9.4.2. Vomiting:
 - 9.4.2.1. From PANO first dose to day +21 post-HCT attribution to study drug is difficult as vomiting is a possible complication of the conditioning regimen and/or rarely due to GVHD.
 - 9.4.2.2. After day + 22 post HCT if a patient develops vomiting grade 3 (increase more than 6 episodes in 24 hours) or grade 4 (life threatening), excluding infection and/or GVHD, it is considered “probable” or “definitive” related to PANO. Protocol specific stopping rules have been formulated for excess GI toxicity (section 12.2).

10. Required Evaluations: Evaluations and study visits are listed in Appendix C.

- 10.1. Demographics:** Ethnic origin, date of birth, gender, primary diagnosis necessitating HCT, HLA-A, B, C, DRB1 matching of donor and recipient, stem cell product (peripheral blood stem cells are only allowed), Date of HCT.
- 10.2. Physical examination:** A directed examination will be performed as per treating physician discretion and based upon patient symptoms. Performance status will be specified by Karnofsky (Appendix D). Comorbidity score (Appendix E).

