12.2. Stopping criteria for toxicity

A patient who receives at least one dose of the study drug (PANO) per protocol is evaluable for toxicity. As shown in Table 9, the accrual will be suspended if c or more of n patients experience CTCAE (v.4) grade 3 or higher toxicity unexpected with transplant, where n is the number of evaluable patients and c is the number of patients who experience CTCAE (v.4) grade 3 unexpected toxicity or higher. Assuming true toxicity rate is 20% and the type I error rate is 5%, the stopping boundary was computed by Ivanova et al⁴⁹. If true toxicity rate is 20%, 40% and 50%, then the probability of early stopping is 4.9%, 79% and 98%, respectively.

Table 9. Boundary for early stopping rule for toxicity

n	3	4	5	6	7	8	9	10	11	12
c	3	4	4	5	5	5	6	6	6	6
n	21	22	23	24	25	26	27	28	29	30
c	9	10	10	10	11	11	11	11	12	12

Note: 1. n = # of patients who receive at least one dose of study drug

2. c = # of patients who experience CTCAE (v4) Grade 3 or higher toxicity unexpected to HCT

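### Section 9.4 says section 12.2 contains stopping rules for excess GI toxicity, but 12.2 does not say whether late grade 3-4 diarrhea or vomiting attributed to PANO counts toward its boundary

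*Combined protocol and SAP*

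**What the plan says.** - **Sections 9.4.1.2 (diarrhea) and 9.4.2.2 (vomiting).** For grade 3 or 4 events after day +22, the diarrhea paragraph reads "excluding infection and/or GVHD, the AE is considered" probably or definitely related to PANO. The vomiting paragraph reads "excluding infection and/or GVHD, it is considered" related in the same terms. Both end with the same cross-reference: "Protocol specific stopping rules have been formulated for excess GI toxicity (section 12.2").
- **Section 12.2.** Accrual is suspended if "c or more of n patients experience CTCAE (v.4) grade 3 or higher toxicity unexpected with transplant". Table 9 note 2 repeats the definition: "c = # of patients who experience CTCAE (v4) Grade 3 or higher toxicity unexpected to HCT". There is no GI term, attribution test or day window. The reference toxicity rate is 20% with 5% type I error. The stated stopping probabilities are 4.9%, 79% and 98% at true rates of 20%, 40% and 50%.
- **Section 9.1 and Table 8.** Section 9.1 presents Table 8 as the description of expected toxicities. Diarrhea and nausea/vomiting are listed there with no grade or day limit. Section 8.8.1 also ties the term to that table: "grade 3 or higher toxicities unexpected for HCT (see table 8"). For listed toxicities, 9.1 adds that "the investigator must use best medical judgment in making an assessment" of whether PANO contributed.
- **Recording.** Section 9.2.1 reports non-hematological toxicities unexpected with HCT. The Table 8 footnote, after dealing with infection and GVHD, says: "Other toxicities will NOT be captured as expected HCT complications". Section 7.2, which names nausea, vomiting and diarrhea, says these effects will be recorded as 9.2 specifies. Section 10.12.3 requires recording of significant findings that meet the AE definition.

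**The concern.** Section 9.4 settles whether a late GI event is related to PANO. The count c in 12.2 depends on a different property, whether the event is unexpected with transplant. Nothing links the two: no passage says that an event attributed to PANO under 9.4 ceases to be expected under Table 8, or that it enters c. A reader who follows 9.4 to 12.2 finds no GI rule, and the only rule there appears to exclude the events that 9.4 describes.

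What is at stake is the trial-level count that suspends accrual. GI events come first among the common non-hematological PANO effects in 7.2. Dosing runs for 26 weeks from day -5 or -6, so most planned exposure falls after day +22. Whether such events count should be fixed before any are seen, not after the count is known.

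Recording turns on the same question. On the literal reading, a non-serious grade 3 event of this kind could go unrecorded under 9.2.1 and the Table 8 footnote; 7.2 and 10.12.3 point the other way.

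**Working it through.** **1. The two readings side by side**

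| Step | Literal reading | Alternative reading |
|---|---|---|
| Is late grade 3-4 diarrhea or vomiting expected? | Yes: listed in Table 8 without grade or day limit | No: Table 8's title covers transplant- or GVHD-related toxicity, and 9.4 attributes these events to PANO |
| Is it an AE under 9.1? | No: 9.1 reserves the term for events unexpected with HCT | Yes: 9.4 is headed as AE attribution and 9.4.1.2 calls late diarrhea an AE (9.4.2.2 uses only a pronoun for vomiting) |
| Does it enter c? | No | Yes, through the general boundary |
| What does the 9.4 cross-reference point to? | Nothing in 12.2 | The general boundary in 12.2 |

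**2. Reproducing the plan's figures**

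Inputs from 12.2: reference rate 20%, type I error 5%. Assumed: 38 patients monitored, the evaluable total in 12.1. The boundary takes c(n) as the smallest k with P(X ≥ k) ≤ 0.0162, where X is binomial(n, 0.20). The level 0.0162 was tuned so that total type I error stays within 5%. The stopping probability comes from an exact patient-by-patient recursion.

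| True rate | Stated | Recomputed |
|---|---|---|
| 20% | 4.9% | 4.9% |
| 40% | 79% | 79.1% |
| 50% | 98% | 97.7% |

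This boundary matches 19 of the 20 Table 9 cells that are visible. The exception is n = 12 (recomputed 7, visible 6), which may be a text-extraction matter. Cells not visible are filled from the recomputed boundary. The printed probabilities therefore belong to the single boundary for unexpected toxicity; no separate GI boundary lies behind them.

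**3. What counting late GI events would change**

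The documents give no late GI rate for 5 mg used as prophylaxis. The available anchors differ:

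- Table 2, 20 mg, not transplant patients: grade 3-4 diarrhea 3.2% plus vomiting 1.3%, so at most 3.2 + 1.3 = 4.5% together.
- Section 1.4, 5 mg as treatment for acute GVHD: the toxicity summary lists no diarrhea or vomiting.
- Section 1.4, post-transplant maintenance study: 25% grade 3/4 GI symptoms of any kind, in 12 patients in dose finding, with dose-limiting toxicity at 20 and 30 mg.

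Assuming independence, combined rate = 1 − (1 − other)(1 − GI). For example, with other 10% and GI 20%: 1 − 0.90 × 0.80 = 0.28.

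| Other unexpected toxicity | Late GI rate | Combined rate | P(suspend), GI not counted | P(suspend), GI counted |
|---|---|---|---|---|
| 10% | 4.5% | 14.05% | 0.2% | 0.8% |
| 10% | 10% | 19% | 0.2% | 3.8% |
| 10% | 20% | 28% | 0.2% | 26% |
| 5% | 4.5% | 9.3% | 0.02% | 0.14% |
| 5% | 10% | 14.5% | 0.02% | 1.0% |
| 5% | 20% | 24% | 0.02% | 13% |

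**4. Sensitivity (other toxicity 10%; late GI 0%, 4.5%, 10%, 20%)**

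- Visible c = 6 at n = 12: 0.20%, 0.90%, 4.0%, 26.6%.
- Same rule run to 44 patients, the expected accrual in 12.1: 0.19%, 0.83%, 4.0%, 29.1%.

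Neither choice alters the picture.

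**The case against.** The strongest reply is that these events already count. Section 12.2 does not cite Table 8, and 8.8.1, which does, governs only the period to day +7. Table 8 is limited by its title to toxicities related to transplant or GVHD. Diarrhea after day +22 with infection and GVHD excluded, and deemed probably or definitely due to PANO, fits that title poorly. Sections 9.4.1.1 and 9.4.2.1 explain the split by day: early attribution is difficult because of conditioning. On this view the specific text in 9.4 qualifies a general list, and the general boundary is the rule that 9.4 means.

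This reading is reasonable and fits the stated intent of 9.4. It still has to be assembled from 9.1, 9.4 and 12.2 against a plain listing in Table 8, and section 9.1 itself uses that table to describe what is expected. The reply shows that the events may be meant to count. It does not show that the text says so.

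Two further points stand and limit the concern. Section 8.9 with Tables 6 and 7 gives patient-level guidance for PANO-related GI symptoms, and 11.7.1 requires reporting of every SAE regardless of suspected causality; both apply on either reading. The effect is also small at the low-rate anchors.

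A reader might infer that the trial has no protection against late GI toxicity, that the investigators would leave these events out, or that 4.9%, 79% and 98% are wrong. The documents support none of these. The patient-level provisions exist, intent is not stated either way, and the printed probabilities reproduce for the event that the boundary counts.

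**Conclusion.** The cross-reference in 9.4 and the event definition in 12.2 are not reconciled. Followed literally, the suspension rule omits the late PANO-attributed GI events that 9.4 says it covers; on another defensible reading it includes them. The gap concerns the trial-level count and possibly the recording of non-serious grade 3 events.

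The consequence depends on a late GI rate that the documents do not give. At 4.5% the choice of reading moves the suspension probability by less than one percentage point. At 20% it moves it from 0.2% to 26% (other toxicity 10%) or from 0.02% to 13% (other toxicity 5%). These figures assume 38 patients monitored, independence of the two kinds of toxicity, and the reconstructed boundary. The point merits correction because a stated safety rule may not do what the protocol says it does, and correction is cheap.

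**What to change.** Reconcile 9.4, Table 8, 9.2.1 and 12.2.

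- **In line with the stated intent of 9.4:** add to 12.2 and to Table 9 note 2 that grade 3-4 GI events attributed to PANO under 9.4 count in c despite their listing in Table 8. Make sure these events are recorded on the CRF. Confirm that the 20% reference rate is meant to cover the combined event.
- **If the investigators do not intend this:** correct the cross-reference in both 9.4 paragraphs, so that neither claims a GI stopping rule in 12.2.

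The cost is one or two sentences of protocol wording and, if the events count, a CRF field. The downside is a little more data entry and a somewhat higher chance of accrual suspension. If other unexpected toxicity were already 20%, counting late GI events at 4.5% (combined 1 − 0.80 × 0.955 = 23.6%) would raise that chance from 4.9% to about 12%. At 10% late GI (combined 28%) it would rise to 26%.

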11.5. Protocol amendments, or changes in study conduct

Any change or addition (excluding administrative) to this protocol requires a written protocol amendment that must be reviewed by Novartis and the investigator before implementation and submission for IRB review. A copy of the written approval of the IRB must be provided to Novartis. Examples of amendments requiring such approval are:

- 11.5.1. increases in drug dose or duration of exposure of subjects,
- 11.5.2. significant changes in the study design (e.g. addition or deletion of a control group),
- 11.5.3. increases in the number of invasive procedures,
- 11.5.4. addition or deletions of a test procedure required for monitoring of safety.

These requirements for approval should in no way prevent any immediate action from being taken by the investigator or by Novartis in the interests of preserving the safety of all patients included in the trial. If an immediate change to the protocol is felt to be necessary by the investigator and is implemented for safety reasons Novartis must be notified and the IRB at the center must be informed immediately. Amendments affecting only administrative aspects of the study do not require formal protocol amendments or IRB approval but the IRB must be kept informed of such administrative changes. Examples of administrative changes not requiring formal protocol amendments and IRB approval include either changes in the staff used to monitor trials or minor changes in the packaging or labeling of study drug.

11.6. Institutional Review Board/Independent Ethics Committee

Before implementing this study, the protocol, the proposed informed consent form and other information to subjects, must be reviewed by a properly constituted Institutional Review Board/Independent Ethics Committee/Research Ethics Board (IRB/IEC/REB). A signed and dated statement that the protocol and informed consent have been approved by the IRB/IEC/REB must be given to Novartis before study initiation. Any amendments to the protocol, other than administrative ones, must be reviewed by Novartis approved by this committee.

11.7. Instructions for data reporting

- 11.7.1. To ensure patient safety, every SAE, regardless of suspected causality, occurring after the patient has provided informed consent and until at least 14 days after the patient has stopped study treatment must be reported to Novartis within 24 hours of learning of its occurrence.

Any SAEs experienced after this 14 days period should only be reported to Novartis if the investigator suspects a causal relationship to the study treatment. Recurrent episodes, complications, or progression of the initial SAE must be

reported as follow-up to the original episode within 24 hours of the investigator receiving the follow-up information. An SAE occurring at a different time interval or otherwise considered completely unrelated to a previously reported one should be reported separately as a new event.

Information about all SAEs is collected and recorded on the Serious Adverse Event Report Form as outlined per contractual agreement; all applicable sections of the form must be completed in order to provide a clinically thorough report. The investigator must assess and record the relationship of each SAE to each specific study treatment (if there is more than one study treatment), complete the SAE Report Form in English, and send the completed, signed form by fax within 24 hours to the oncology Novartis Drug Safety and Epidemiology (DS&E) department.

The telephone and telefax number of the contact persons in the local department of Drug Safety and Epidemiology (DS&E) are included in the contractual agreement. The original copy of the SAE Report Form and the fax confirmation sheet should be kept with the case report form documentation at the study site.

Follow-up information is sent to the same contact(s) to whom the original SAE Report Form was sent, using a new SAE Report Form stating that this is a follow-up to the previously reported SAE and giving the date of the original report. Each re-occurrence, complication, or progression of the original event should be reported as a follow-up to that event regardless of when it occurs. The follow-up information should describe whether the event has resolved or continues, if and how it was treated, whether the blind was broken or not, and whether the patient continued or withdrew from study participation.

If the SAE is not previously documented in the Investigator's Brochure or Package Insert (new occurrence) and is thought to be related to the Novartis study treatment, an oncology Novartis Drug Safety and Epidemiology (DS&E) department associate may urgently require further information from the investigator for Health Authority reporting. Novartis may need to issue an Investigator Notification (IN), to inform all investigators involved in any study with the same drug that this SAE has been reported. Suspected Unexpected Serious Adverse Reactions (SUSARs) will be collected and reported to the competent authorities and relevant ethics committees in

accordance with Directive 2001/20/EC or as per national regulatory requirements in participating countries.

- 11.7.2. Pregnancies: To ensure patient safety, each pregnancy occurring while the patient is on study treatment must be reported to Novartis within 24 hours of learning of its occurrence. The pregnancy should be followed up to determine outcome, including spontaneous or voluntary termination, details of the birth, and the presence or absence of any birth defects, congenital abnormalities, or maternal and/or newborn complications.

Pregnancy should be recorded on a Clinical Trial Pregnancy Form and reported by the investigator to the oncology Novartis Drug Safety and Epidemiology Department (DS&E). Pregnancy follow-up should be recorded on the same form and should include an assessment of the possible relationship to the panobinostat any pregnancy outcome. Any SAE experienced during pregnancy must be reported on the SAE Report Form.

Pregnancy outcomes must be collected for the female partners of any males who took study treatment in this study. Consent to report information regarding these pregnancy outcomes should be obtained from the mother.

- 11.8. Data review and management:** The Principal Investigator and the Clinical Trial Coordinator(s) assigned to the case will be primarily responsible for maintaining all study related documents including clinical research forms, as applicable. The Principal Investigator has the ultimate responsibility. Investigators must enter the information required by the protocol onto Case Report Forms (CRFs). ONCORE is the database of record for all CRF entries and will be verified with source documentation. The review of medical records within PowerChart will be done in a manner to assure that patient confidentiality is maintained. Data collected will be stored in a secure BMT program database and Moffitt Cancer Center's database system, ONCORE. Identifying patient information will be kept confidential. Representatives of the USF IRB and the FDA will have access to patient information as it pertains to the study. Privacy and confidentiality of the information will be protected to the extent provided by law.

12. Statistical methods

